6.2. TEMPORAL CHANGES IN CLINICAL CHARACTERISTICS (Research Question 1.3)

Another research question focuses on assessing potential temporal changes in the demographic and clinical characteristics of youth with diabetes over time. Analysis of variance (for continuous measures like age and HbA_{1c}) and logistic regression (for dichotomous measures like prevalence of autoimmunity) will be used to assess changes in these outcomes over time. Time will initially be entered as a categorical variable to check for any differences over time. Time will then be considered continuously to check for consistent changes over time (slopes). Time by covariate interactions will be assessed to

determine if the slopes differ by level of important covariates (e.g., does the change in age over time differ for males and females). In Table 6.2, we show the slopes that can be detected with 80% power using the data through 2014, assuming that 1) onset age will be available each year and data for the other measures will be available for cohorts incident in 2002-2006, 2008, and 2012; 2) the sample sizes for onset age and for variables of interest among T2D youth will remain constant; and 3) the sample size for variables of interest among T1D youth will remain constant between 2002 and 2008 and will be 5/6(N) for 2012 (due to sampling only 50% of the NHW age <10 years). For example, there are about 970 incident T1D cases per year with an IPV in our surveillance area. The mean age of newly diagnosed T1D cases in 2002 was 9.4 years with a standard deviation of 4.7 years. Using data through 2014, we can detect a yearly change in onset age of 0.031 years (e.g., 9.4 in 2002 vs 9.0 in 2014). Approximately 84% of T1D had evidence of autoimmunity in 2002. With a sample size of approximately 440 for diabetes autoimmunity each year it is collected, we'll be able to detect a change of 0.6% per year (e.g., 84% in 2002 vs 90% in 2012).

Table 6.2 - Changes in Clinical Presentation, By Type, Detectable with 80% Power in 2014						
Variable	Mean (SD)	N per year	Detectable change			
T1D						
Onset Age (years)	9.4 (4.7)	970	0.031			
BMI-z	0.6 (1.0)	500	0.015			
HbA_{1c} (%)	7.9 (1.6)	470	0.025			
Insulin Sensitivity	10.3 (3.3)	430	0.054			
FCP (ng/ml)	0.5 (0.5)	470	0.008			
Autoimmunity (%)	84% (36%)	440	0.006			
DKA (%)	30% (46%)	760	0.006			
T2D						
Onset Age	14.3 (2.8)	250	0.037			
BMI_z	2.1 (0.7)	85	0.026			
HbA _{1c}	7.5 (2.4)	85	0.088			
Insulin Sensitivity	4.6 (2.8)	75	0.109			
FCP (ng/ml)	3.3 (1.9)	85	0.069			

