Research Question 1.3: Are there temporal changes in the clinical characteristics at onset of diabetes in youth and how do these differ by a) clinical diabetes type (T1D versus T2D); b) race/ethnicity (non-Hispanic white versus minority); and c) sex (males versus females)?

Specific characteristics to be examined are: age at onset of diabetes, markers of disease severity (diabetic ketoacidosis, residual insulin secretion, HbA_{1c}), immunogenetic markers (diabetes autoantibodies, HLA risk genotypes), markers of insulin sensitivity (insulin sensitivity score, waist circumference, body mass index), cardio-vascular risk factors (lipid profile, blood pressure, microalbuminuria).

Aim 2: To provide consultation and support to inform the development of low-cost sustainable public health surveillance systems of childhood diabetes in the U.S., with a focus on challenges in ascertainment of cases with T2D and cases among older youth (ages 15 years or older) with any form of non-gestational diabetes.

Research Question 2.1: Within the SEARCH surveillance system, what factors contribute to time from diagnosis to case ascertainment? Can an extended period of time to case ascertainment be accounted for by the time to receipt of specialty care or hospitalization? Are there temporal changes in time to case ascertainment?

Research Question 2.2: Within and across health care systems, using the same case ascertainment algorithm, are patterns of care different for youth with T2D or older youth with any type of diabetes, around the time of clinical diagnosis, and thereafter? Are there temporal changes in observed differences, both within and across systems?

Aim 3: Assess total and cause-specific mortality among 2002-2008 incident cases for the period from the date of diabetes diagnosis through December 31, 2010.

Research Question 3.1: Are the frequency and causes of mortality in youth with diabetes different than non-diabetic, age comparable youth? Among youth with diabetes, does the frequency of mortality differ by type of diabetes, race/ethnicity or other socio-cultural factors?

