In-Person Research Visit (IPV): The IPV or "registry visit" in SEARCH 3 is designed to collect data on relevant dimensions of diabetes type (presence of autoimmunity, genetic susceptibility to autoimmunity, insulin sensitivity, insulin secretion) and data informing the clinical presentation of diabetes. We will also store (by separate consent) blood, serum, plasma and urine for future genetic and non-genetic analyses. In keeping with the time-stratified sampling approach initiated in SEARCH 2, only the incident 2012 cohort will be eligible to participate in the registry visit. An additional sampling approach will be implemented in SEARCH 3, in order to reduce participant burden and maximize study resources, without compromising the statistical power to detect trends in clinical characteristics over time. To maximize the number of minority participants and youth with T2D, eligible cases for SEARCH 3 registry visit are all cases >10 years old, regardless of ethnicity/race, all minority cases, regardless of age, all cases not T1, regardless of race or age, and 50% of NHW T1 cases <10 years old. Since some sites are not able to obtain race at the time of the assignment of the PID, if race is not available, all participants will be invited to the IPV. We will seek a 70% completion of the IPV among eligible youth.

Table 5-1: Summary of SEARCH3 Registry Data Collection						
	Eligible Cohorts	Core Variables	Clinical Presentation			
MRA	2010-2014	Date of birth, date of diagnosis, sex, provider- determined diabetes type, race/ethnicity, residence in the year of diagnosis	Weight/height at diagnosis, DKA at diagnosis, insulin use, acanthosis nigricans, diabetes autoantibodies and c-peptide assessment			
IPS	2010-2014	Date of birth, date of diagnosis, sex, self-reported race/ethnicity, residence in the year of diagnosis; health insurance; usual diabetes care, education of parents; youth > 18 yrs.	Treatment history, secondary diabetes, symptoms at presentation, acute complications, medications, family history, contact information; reported height, weight			
IPV	2012		 Physical Exam: height, weight, waist circumference, BP, acanthosis nigricans Medication Inventory: list of currently prescribed medications Lab/specimens: diabetes autoantibodies (GAD65, IA2), HbA_{1c}, fasting glucose, C-peptide, lipids, urinary albumin/creatinine (spot sample) Repository: serum, plasma, DNA (by separate consent) and urine for storage on 1st morning void 			

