The content of the IPV for incident cases will be similar to SEARCH 1 and 2 (Table 5 - 1). However, unique to SEARCH 3, we will add a first morning void urine collection that the participant will bring to the clinic. Urinary albumin and creatinine will be measured to obtain an albumin/creatinine ratio on a spot urine sample. Samples will not be collected during the visit on participants who are pregnant or menstruating, have had a fever greater than 100 degrees in the past two hours, or who have taken an antibiotic in the past seven days for a urinary tract infection. A dipstick test will also be performed to test for the presence of blood or leukocytes by the central laboratory. Urine will also be stored (first morning void only) to assess other markers of nephropathy in the future. (8/11)

The following will be collected for the IPV incident cases: fasting blood and urine for laboratory measurements and storage, and a brief physical examination as outlined below.

• Blood measures: Diabetes autoantibodies (GAD65, IA-2); (ZNT8 will be added after the assay is standardized); HbA_{1c}, fasting glucose and C-peptide, lipids (total

cholesterol, HDL-Cholesterol, LDL-Cholesterol, triglycerides), HLA risk genotypes

- Urine measures (spot and first morning void): Urinary albumin and creatinine (from spot urine collection)
- Physical examination: Height, weight, blood pressure, assessment of acanthosis nigricans, waist circumference (NHANES and minimum waist methods) on participants who are 3 years of age or older at the time of the visit
- Medication inventory: List of currently prescribed medications.

SEARCH participants with an IPS will be invited to complete the IPV if they meet the following eligibility criteria. If <10 years of age and have type 1 diabetes, we will invite 50% of non-Hispanic White and 100% of all minority youth to participate in the IPV. All youth with type 2 diabetes will be invited to the visit. To encourage IPV participation, a remuneration of \$80.00 in cash or gift cards will be offered. Some centers may offer assistance with transportation in order to facilitate these visits. We will seek to complete a 70% rate among those participants invited to the IPV (Table 5-2).

Table 5-2. Estimated Number of Cases Registered, and Participating in the IPS and IPV								
Per Year								
Center	Estimated 2	N Incide	nt cases/year	Estimated N	Estimated N			
	NHW<10	Other	Total	IPS/year	IPV/year*			
SC	70	206	276	248	179			

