6.1.3. Longitudinal Models

All participants in the SEARCH Cohort Study will have already had at least one inperson visit during SEARCH 1 and 2, and ~75% of the 2002-2005 incidence cases have at least 2 in-person visits per the SEARCH 2 protocol. Since SEARCH 2 also included longitudinal data (there are over 2000 SEARCH participants already with at least one follow-up visit), our team developed a plan for modeling longitudinal data. Specifically, we will use longitudinal mixed effects analysis of covariance models that always include duration of diabetes as a time-varying covariate. This approach correctly models the varying durations of disease prior to the initial SEARCH in-person visit, and the varying

Section 6B - Statistical Considerations (Phase 3 - 12/2010) Cohort Study

durations of time allowed via the SEARCH data collection windows between the initial and subsequent visits.

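### Registry trends in C-peptide, HbA1c and similar visit measures are labelled as at onset but modelled on calendar time without diabetes duration, so a change in visit delay could pass for a trend

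*Protocol*

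**What the plan says.** Section 4A 4.1.1, Research Question 1.3, asks: "Are there temporal changes in the clinical characteristics at onset of diabetes in youth". The characteristics listed include residual insulin secretion, HbA1c, autoantibodies and insulin sensitivity.

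Section 5A 5.1.2 takes the laboratory measures from the in-person visit: "The following will be collected for the IPV incident cases: fasting blood and urine for laboratory measurements and storage". Invitation follows registration and a completed initial survey. In Phase 3, "only the incident 2012 cohort will be eligible to participate in the registry visit". I found no limit on the interval from diagnosis to visit.

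Section 6A 6.2 confirms the source for the trend analysis. Onset age is available every year, whereas "data for the other measures will be available for cohorts incident in 2002-2006, 2008, and 2012". The stated model is analysis of variance or logistic regression on calendar time: "Time will initially be entered as a categorical variable to check for any differences over time". Time is then made continuous, and time-by-covariate interactions are tested. Diabetes duration is not mentioned.

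Section 6B 6.1.3 handles the first SEARCH visit differently in the Cohort Study. It specifies "longitudinal mixed effects analysis of covariance models that always include duration of diabetes as a time-varying covariate" and gives the reason: "This approach correctly models the varying durations of disease prior to the initial SEARCH in-person visit".

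**The concern.** A measure taken some months after diagnosis reflects both the state at onset and what has happened since. If the average delay is the same in every incident year, the second part cancels from a calendar trend. If it changes, a model with calendar time alone puts the difference into the slope.

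The protocol supplies most of this argument itself. Section 6B says duration before the first visit varies. Cohort Research Question 3.1 treats the dimensions of diabetes type as evolving. Section 8A 8.7.5 builds the insulin sensitivity index partly from HbA1c, so that index would inherit any duration effect on HbA1c. Registry Research Question 2.1 leaves drift open: "Are there temporal changes in time to case ascertainment". Section 6A 6.4 asks whether ascertainment takes longer for type 2 cases and older youth. Section 5A 5.1.2 also plans re-ascertainment of the 2008-2012 cohorts in 2014, without saying whether 2012 cases registered late may still attend the visit.

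At stake is whether a reported change in residual insulin secretion or HbA1c describes presentation or merely the timing of the visit. The 2012 cohort matters most: it is the only Phase 3 visit cohort in Sections 5A and 6A, and it lies four years after the next latest.

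**Working it through.** **Inputs (Section 6A, Table 6.2 and text).** Visit cohorts 2002-2006, 2008 and 2012. Type 1: C-peptide SD 0.5 ng/ml, HbA1c SD 1.6 points, N 470 per year, detectable slopes 0.008 and 0.025 per year. Type 2: C-peptide SD 1.9, HbA1c SD 2.4, N 85, detectable slopes 0.069 and 0.088. Power 80%; two-sided 5% as stated in 6.1.

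**Step 1: reproduce the plan's slopes.** Detectable slope = (1.96 + 0.84) × SD / √(N × Σ(t − t̄)²). With seven equal cohorts, t̄ = 2005.71 and Σ(t − t̄)² = 69.43.

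- Type 1 HbA1c: 2.80 × 1.6 / √(470 × 69.43) = 0.0248 (table 0.025).
- Type 1 C-peptide: 2.80 × 0.5 / √(470 × 69.43) = 0.0078 (table 0.008).
- Type 2 HbA1c: 0.0875 (table 0.088). Type 2 C-peptide: 0.0693 (table 0.069).

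The table is reproduced. The text says the 2012 type 1 sample is 5/6 of N; that would give 0.0261 for HbA1c, so the reduction seems not to have been applied. This is minor.

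**Step 2: leverage of 2012.** If only the 2012 mean moves by one unit, the slope moves by c = w₂₀₁₂ × (2012 − t̄) / Σw(t − t̄)², where w is the relative sample size.

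- 2012 at 5/6 of N: t̄ = 2005.56, sum = 62.68, c = 0.0856 per year.
- 2012 at full N: c = 6.286 / 69.43 = 0.0905 per year.

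Using 0.0856 for type 1, the 2012 shift that equals the detectable slope is 0.008 / 0.0856 = 0.093 ng/ml for C-peptide and 0.025 / 0.0856 = 0.29 points for HbA1c.

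**Step 3: convert to months of delay (type 1).** The documents give no rates of change with duration. I assume 0.01-0.03 ng/ml per month for C-peptide and 0.03-0.10 points per month for HbA1c.

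| Measure | 2012-only shift | Linear drift, 2002-2012 |
|---|---|---|
| C-peptide | 3.1-9.4 months | 0.08 / (0.03 to 0.01) = 2.7-8.0 months |
| HbA1c | 2.9-9.7 months | 0.25 / (0.10 to 0.03) = 2.5-8.3 months |

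**Step 4: false-positive rate for a 3-month shift in 2012 and no true trend (type 1).** The standard error is the detectable slope / 2.80: 0.00286 for C-peptide and 0.00892 for HbA1c.

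- C-peptide: bias 0.0856 × 3 × (0.01 to 0.03) = 0.0026 to 0.0077, or 0.90 to 2.70 standard errors. The 5% test rejects 15% to 77% of the time.
- HbA1c: bias 0.0856 × 3 × (0.03 to 0.10) = 0.0077 to 0.0257, or 0.86 to 2.88 standard errors. It rejects 14% to 82% of the time.

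**Step 5: type 2.** Section 6A 6.2 keeps the type 2 sample constant, so c = 0.0905. The shifts needed are 0.069 / 0.0905 = 0.76 ng/ml and 0.088 / 0.0905 = 0.97 points. At the Step 3 rates these are 25-76 months (C-peptide) and 10-32 months (HbA1c). With steeper assumed rates (0.2-0.5 ng/ml and 0.5-1.5 points per year) and linear drift, 0.69 ng/ml and 0.88 points correspond to about 17-41 and 7-21 months.

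**Step 6: cost of adjustment.** Adding duration multiplies the detectable slope by 1 / √(1 − R²), where R² is that between duration and incident year. Assuming R² of 0.01-0.10, the factor is 1.005-1.054; HbA1c goes from 0.0248 to at most 0.0261.

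**The case against.** - **Silence is not exclusion.** Section 6A 6.2 is short, gives no adjustment list, and does not rule duration out; an SAP could add it. This stands as a limit. What remains is that the model stated for this question omits a term that the sister section says it always includes, and that the visit window and the at-onset label are protocol matters.
- **Comparability is planned for.** Section 5A keeps ascertainment methods the same as in Phases 1 and 2 and flags cases registered outside the standard window. Section 6A 6.4 measures months from diagnosis to registration by type and age. This makes drift less likely and partly visible. It concerns registration delay, however, not visit delay, and does not feed into the 6.2 model.
- **Some data are nearer to diagnosis.** Table 5-1 of Section 5A lists autoantibodies and C-peptide under medical record abstraction, and Section 4A 4.2.3.1 says autoantibodies are collected near diagnosis. The first is correct, but 6.2 restricts the analysis to the visit cohorts; the second gives no window.
- **The rates are assumed.** Section 4A 4.2.3.3 links preserved C-peptide in the first year to older onset age and lower HbA1c, but gives no rate of change. This stands: the months above are illustrative.

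A reader might infer that visit delay has in fact drifted, or that every visit measure is affected. The documents support neither. Asking whether ascertainment time changes is not evidence that visit delay did. HLA genotype cannot change with duration, and nothing in the protocol shows lipids changing with early duration.

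**Conclusion.** The point holds as a gap in the stated model, with moderate confidence; correcting it is a cheap improvement. For C-peptide, HbA1c and other duration-sensitive visit measures, the plan asks about onset, measures at a visit of varying and unbounded timing, and omits duration from the trend model, while the Cohort section recognises the same feature and adjusts for it.

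The bias is conditional: it arises only if mean delay differs between 2012 and 2002-2008, and its existence, direction and size cannot be read from the documents. Under the assumed type 1 rates, about 3 to 10 months of shift in 2012 alone would equal the detectable slope. Type 2 is much less exposed, so it would be too strong to say that trends in both types are equally vulnerable. Onset age, DKA, HLA and chart-abstracted values at diagnosis are unaffected.

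The leverage figure takes 2012 as the visit cohort, as Sections 5A and 6A do. Sections 8A 8.2 and 8.7.5 name 2011 and 2013 instead; these sections must be reconciled.

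**What to change.** In Section 6A 6.2:

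- Add diabetes duration at the visit (visit or specimen date minus diagnosis date), in a flexible form, to the models of C-peptide, HbA1c and other duration-sensitive visit measures. Leave out onset age, DKA, HLA and chart-abstracted values at diagnosis.
- Report the distribution of visit delay by incident year and diabetes type.
- Add a sensitivity analysis restricted to one diagnosis-to-visit window common to all cohorts, with its length fixed beforehand.
- Describe these outcomes as measured at the baseline visit, and keep the at-onset label for values recorded at diagnosis.

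No new data are needed: Section 5A 5.1.2 registers the diagnosis date and Section 8A 8.8 ties specimens to their collection date. The cost is a detectable slope larger by about 0.5-5% under the R² range assumed in Step 6, and fewer cases in the windowed analysis.

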5.1 AIM 1: TEMPORAL TRENDS

5.1.1. Overview of Design, Methods and Data Collection

Centers in SEARCH Phase 3 will continue to conduct population-based ascertainment of cases of diabetes in youth less than 20 years of age in the year of diagnosis for the period 2010 - 2014, using methods consistent with those employed in SEARCH Phase 1 and SEARCH Phase 2. This will involve identification, validation, confirmation of eligibility and uniqueness of cases, and registration of the case both locally with identifiers and centrally with the SEARCH 3 Coordinating Center (CoC) without identifiers. The 2010 - 2014 cases will have their medical records abstracted and will be asked to complete a brief survey. A sample of 2012 cases will be invited to an in-person research visit. Case registration will proceed without disruption in the transition from the end of SEARCH Phase 2 (September 29, 2010) until the full implementation of the SEARCH Phase 3 protocol. All data collection will be performed under standardized protocols by centrally trained and certified staff.

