Medical Record Abstraction (MRA) serves the following purposes: a) validation of diabetes diagnosis; b) main source of core demographic and diagnostic information, and c) secondary data source for race/ethnicity information. In SEARCH 2, an additional set of items pertinent to clinical presentation was added to the medical record abstraction effort: weight/height at diagnosis, DKA at diagnosis and insulin use history. We will continue to collect these data through MRA in SEARCH 3 and will seek 100% completion.

Initial Participant Survey (IPS) contains key data, including the core information described above, and serves to: a) verify of case eligibility (e.g., residence in the year of diagnosis); and b) is the main source for self-reported race/ethnicity information. Additional information includes: symptoms at presentation, potential secondary causes of the diabetes, use of insulin and other medications, treatment history, family structure, usual language spoken, and contact information (for local use only). The IPS can be self-administered or interviewer-administered. The information can be collected online, by phone or in person, or at the beginning of the in-person research visit. To encourage participation in the IPS, a monetary incentive of \$10.00 will be offered. We will continue to collect these data through IPS in SEARCH 3 (Table 5 - 1) and will seek 90% completion.

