Regression models will also be used to assess differences in the slopes by demographic characteristics (i.e, covariate by time interactions). Table 6.1 shows the differences in slopes of T1D and T2D, by demographic characteristics, which we can detect in 2014 (e.g., males vs females, NHW vs minority, and 0-9 vs 10-19 for T1D or 10-14 vs 15- 19 for T2D) with 80% power at the 5% two-sided level of significance, assuming a variety of slopes. For slopes ranging from 0.2 to 0.5 the detectable differences between groups are almost identical. We see that for T1D, using data through 2014, we can detect a difference in slopes of 0.28. The detectable differences in the slopes of T2D diabetes are slightly larger because of the smaller denominator (youth 10 and older), but not much larger since there is a lower incidence of T2D. Note that the most conservative estimates are shown in Table 6.1 (e.g., NHW vs minority for T1D as the denominators differed most for these groups); detectable differences were similar for other group comparisons.

Table 6.1 - Differences in slopes detectable with 80%								
power in 2014 (betw	power in 2014 (between genders, races, and age groups)							
Slope 1*	Slope 1* Slope 2* Difference							
T1D	T1D							
0.20	0.47	0.27						
0.30	0.30 0.58 0.28							
0.40 0.68 0.28								
0.50 0.78 0.28								
T2D								
0.20	0.20 0.52 0.32							
0.30	0.63	0.33						
0.40	0.74	0.34						
0.50 0.84 0.34								
* Slope 1 is the observed slope in one group (e.g., males;								
NHW; etc) and Slope 2 is the observed slope in the other								
group (e.g., females; Other; etc)								

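### Table 6.2 works out the detectable T1D trend in DKA at onset from the visit cohorts alone, although DKA is abstracted from records for all 2010-2014 cases; the stated 0.006 per year is about 70% too large

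*Protocol*

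**What the plan says.** Section 6A, 6.2 introduces Table 6.2 as follows: "we show the slopes that can be detected with 80% power using the data through 2014". It then lists its assumptions. Onset age is taken as available every year. For everything else, "data for the other measures will be available for cohorts incident in 2002-2006, 2008, and 2012". The T1D sample size is held constant from 2002 to 2008 and "will be 5/6(N) for 2012 (due to sampling only 50% of the NHW age <10 years"). The DKA row reads "DKA (%) 30% (46%) 760 0.006": 30% prevalence, SD 0.46, 760 T1D cases per year, detectable change 0.006 per year.

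Section 5A describes how DKA is collected. In 5.1.1: "The 2010 - 2014 cases will have their medical records abstracted and will be asked to complete a brief survey". Table 5-1 puts the following in the medical record abstraction (MRA) row, for cohorts 2010-2014: "Weight/height at diagnosis, DKA at diagnosis, insulin use, acanthosis nigricans". DKA does not appear in the in-person visit row, which covers 2012 only. Section 5.1.2 says that DKA, together with weight and height at diagnosis, joined the abstraction in SEARCH 2, and adds: "We will continue to collect these data through MRA in SEARCH 3 and will seek 100% completion".

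**The concern.** The list of cohorts and the five-sixths factor are rules about who attends a visit. Section 6A applies them to a measure that Section 5A takes from the chart of every registered case. Table 6.2 itself hints at a source beyond the visit: DKA has 760 T1D cases per year, while the other T1D rows apart from onset age have 430 to 500.

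DKA at onset is a named severity marker for Research Question 1.3. Section 6.2 is the only place in the protocol that says which years support that question. If its availability statement is wrong for DKA, the stated sensitivity of that trend is wrong too. An analyst who took the statement as the data definition would use one Phase 3 cohort where five are collected.

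**Working it through.** **Inputs.** From Table 6.2: SD 0.46, 760 per year, 80% power, stated change 0.006. From the text of 6.2: the seven cohorts and the factor 5/6 for 2012. The significance level is not given for Table 6.2; I assume the one given for Table 6.1, "with 80% power at the 5% two-sided level of significance". I also assume 760 cases in each added year.

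**Formula.** For a least-squares slope on calendar year:

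- detectable slope = (1.960 + 0.842) × SD / √S, where S = Σ n_y (year − weighted mean year)²
- power at slope b = Φ(b√S/SD − 1.96)

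**Check of the method on other rows.** Onset age in T1D, 13 years at 970: S = 970 × 182, giving 2.80 × 4.7/√176,540 = 0.0313 (stated 0.031). The T2D visit rows on seven equal cohorts give 0.0255, 0.0875, 0.1087 and 0.0693 (stated 0.026, 0.088, 0.109 and 0.069).

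**The stated DKA row.** Count years from 2002, so the cohorts are 0, 1, 2, 3, 4, 6 and 10, with weight 1 each and 5/6 for the last.

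- Total weight 6.833; weighted sum 24.333; weighted sum of squares 149.333
- 149.333 − 24.333²/6.833 = 62.68, so S = 760 × 62.68 = 47,639
- Standard error 0.46/√47,639 = 0.00211; detectable slope 0.0059, which rounds to the stated 0.006
- Power at 0.005 per year: Φ(2.372 − 1.96) = 66%

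Thirteen years at 760 would give 0.0035, so the printed figure does rest on the seven cohorts. Keeping 2012 at the full 760 gives 0.0056, which also rounds to 0.006, so the rounded row alone cannot show whether the factor was applied. The text says that it was.

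**With the 2010-2014 abstraction.** The years become 0, 1, 2, 3, 4, 6, 8, 9, 10, 11 and 12, at 760 each.

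- Sum 66; sum of squares 576; 576 − 66²/11 = 180, so S = 136,800
- Standard error 0.46/√136,800 = 0.00124; detectable slope 0.0035 (0.00348)
- Power at 0.005 per year: Φ(4.020 − 1.96) = 98%

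**Size of the error.** 0.006/0.00348 = 1.72. Unrounded, 0.0059/0.00348 = 1.69. With constant N in the baseline, 0.0056/0.00348 = 1.61.

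**Sensitivity.**

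| Years and N | Detectable change per year |
|---|---|
| 11 cohorts, 2012 still at 5/6 | 0.00351 |
| All 13 years (2007 and 2009 added), 760 | 0.00347 |
| 11 cohorts, 970 per year from 2010 | 0.0033 |
| All 13 years, 970 | 0.0031 |

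Whether 2007 and 2009 have DKA data hardly matters.

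**The case against.** **It is a power-table assumption, not an analysis rule.** This stands. A reader might infer that the DKA trend will be analysed on seven cohorts and the other years thrown away. The documents do not say so. The analysis text in 6.2 (logistic regression, with time categorical and then continuous) restricts no outcome to visit years, and Aim 1 covers 2002-2014. What is wrong is the stated availability and the figure built on it.

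**The error is conservative.** This also stands. The row understates power, and no sample size or eligibility rule depends on it.

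**The gain may depend on early data that do not match.** DKA was added to the abstraction only in SEARCH 2, and the protocol does not date that change. If usable DKA data began with the 2006 cohort, nine years at 760 would give S = 760 × 60 and a detectable slope of 0.0060, with 64% power at 0.005: no better than the printed row. This limits how firmly 0.0035 can be stated. It does not rescue the row, because Table 6.2 already counts 760 DKA records in each of 2002-2006 and 2008, and Section 1 says that incident cases in Phases 1 and 2 had record review. On the table's own premise, the Phase 3 years add to those cohorts.

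**Full completion is a target.** True. 760 of about 970 T1D cases is roughly 78%, which is why the calculation keeps 760 and not 970.

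**Sampling bias in 2012.** A reader might also infer that the 2012 point will be biased because half of the non-Hispanic white T1D cases under 10 are not invited to the visit, and Section 4A reports the highest DKA frequencies at the youngest ages (37% at 0-4, 27% at 5-9). That would follow only if DKA in 2012 were taken from the visit sample. Section 5A says that it comes from records, which are not sampled.

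**Conclusion.** The point holds as an inconsistency between Section 6A, 6.2 and Section 5A, with a misstated figure as its result. For T1D, Table 6.2 gives a detectable DKA trend of 0.006 per year. The planned data collection supports about 0.0035, so the stated value is about 70% too large (range 61% to 73% over the baselines and year sets shown). For a change of 0.5 percentage points per year, power is 98% where the stated design has 66%.

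This rests on three assumptions: a two-sided 5% level, as for Table 6.1; 760 T1D cases with DKA data in each added year; and DKA data for 2002-2006 and 2008 that are comparable with the later abstraction. The last matters most and should be confirmed. The study is not put at risk, since the error understates what it can detect, but the correction is worth making.

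**What to change.** In Section 6A, 6.2:

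1. Limit the seven-cohort assumption and the 5/6 factor to measures that exist only at the in-person visit.
2. State that the DKA trend uses record-abstracted DKA on all registered cases in every year in which it is available: the 2002-2006 and 2008 data already assumed, 2010-2014, and 2007 and 2009 if abstracted. Say whether the earlier DKA data were collected in the same way.
3. Restate the DKA row of Table 6.2: about 0.0035 per year at 760 cases per year, or the value for the availability actually confirmed.

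The cost is a few sentences and one recomputed row. No data collection changes.

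### Table 6.2 states a 5/6 sample for type 1 diabetes in 2012, but its detectable slopes were computed at constant N; three entries are about 5% too small under that assumption

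*Protocol*

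**What the plan says.** Section 6A, 6.2, introduces Table 6.2 with the words "we show the slopes that can be detected with 80% power using the data through 2014". Three assumptions follow:

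- Onset age is known every year, and "data for the other measures will be available for cohorts incident in 2002-2006, 2008, and 2012".
- "the sample sizes for onset age and for variables of interest among T2D youth will remain constant".
- For the remaining T1D variables, "the sample size for variables of interest among T1D youth will remain constant between 2002 and 2008 and will be 5/6(N) for 2012". The text attributes the reduction to sampling half of the non-Hispanic white cases under 10.

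Table 6.2 then prints, for T1D, the rows "BMI-z 0.6 (1.0) 500 0.015" and "HbA_{1c} (%) 7.9 (1.6) 470 0.025" (mean, SD, N per year, detectable change), and insulin sensitivity with SD 3.3, N 430 and detectable change 0.054.

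Section 5A, 5.1.2, describes the same sampling as reducing burden "without compromising the statistical power to detect trends in clinical characteristics over time".

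**The concern.** The third assumption exists so that the T1D figures carry the cost of the sampling. If the reduction was written down but not entered into the calculation, those rows answer a different question from the one in the text, and the stated 80% does not belong to the printed slopes. The reduction falls in the last year of the series, far from the other years. It removes 1/6 of one year in seven, 1/42 or about 2.4% of the observations, but about 10% of the information on the slope. At stake is the accuracy of a planning table. No sample size or analysis depends on it.

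**Working it through.** **Inputs.** SD, N per year and printed slope come from Table 6.2. Years are 2002–2006, 2008 and 2012 (Section 6.2). Power is 80%. Table 6.2 states no significance level; I carry over the one given for Table 6.1 in Section 6.1, "with 80% power at the 5% two-sided level of significance". This is an assumption, but it reproduces every row.

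**Formulas** (linear slope over calendar year):

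- Detectable slope = (1.9600 + 0.8416) × SD / √(N × Sxx) = 2.8016 × SD / √(N × Sxx)
- Power at slope d = Φ(d × √(N × Sxx) / SD − 1.96)
- Sxx = Σ w(year − weighted mean)², with w the year's sample as a fraction of N

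**Sxx**, with years coded 0, 1, 2, 3, 4, 6, 10:

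- Constant N: 166 − 26²/7 = 69.43
- 5/6 N in 2012: 149.33 − 24.33²/6.833 = 62.68
- Onset age, 2002–2014, constant N: 182

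**Step 1: rows for which the protocol itself states constant N.** The type 2 rows give 0.02553, 0.08753, 0.10871 and 0.06929, printed as 0.026, 0.088, 0.109 and 0.069. The onset-age rows give 0.03134 (T1D) and 0.03678 (type 2), printed as 0.031 and 0.037. All six agree, so the method is the protocol's own.

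**Step 2: the other T1D rows under both weightings.** Example, BMI-z: 2.8016 × 1.0 / √(500 × 69.43) = 0.01504 at constant N; 2.8016 × 1.0 / √(500 × 62.68) = 0.01583 with 5/6 N in 2012.

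| T1D row | SD | N | Printed | Constant N | 5/6 N in 2012 | Power at printed slope, 5/6 N |
|---|---|---|---|---|---|---|
| BMI-z | 1.0 | 500 | 0.015 | 0.01504 | 0.01583 | 75.7% |
| HbA1c | 1.6 | 470 | 0.025 | 0.02481 | 0.02612 | 76.5% |
| Insulin sensitivity | 3.3 | 430 | 0.054 | 0.05351 | 0.05631 | 76.6% |
| C-peptide | 0.5 | 470 | 0.008 | 0.00775 | 0.00816 | 78.4% |
| Autoimmunity | 0.36 | 440 | 0.006 | 0.00577 | 0.00607 | 79.0% |
| DKA | 0.46 | 760 | 0.006 | 0.00561 | 0.00590 | 81.2% |

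All six round to print at constant N. With 5/6 N, the first three do not.

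**Step 3: can another reading reach the printed values with 5/6 N?** Results are in the order BMI-z, HbA1c, insulin sensitivity.

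- One-sided 5%: 0.0141, 0.0232, 0.0500. No match.
- Table N taken as the seven-year mean: 0.0156, 0.0258, 0.0556. No match.
- Most favourable input rounding (SD lower by 0.05, N higher by 5): 0.01496, 0.02517, 0.0551. The first two would print as 0.015 and 0.025. Insulin sensitivity would print as 0.055, not 0.054.

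**The case against.** Several points against a stronger statement are sound.

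- A reader might infer that every T1D row exposes the omission. It does not. C-peptide, autoimmunity and DKA round to the printed value under either weighting, and DKA keeps more than 80% power at its printed slope.
- Table 6.2 prints rounded inputs. Rounding alone could explain BMI-z and HbA1c, so taken singly only insulin sensitivity is inconsistent with the 5/6 assumption. Constant N remains the simpler account, since it fits all twelve rows without adjustment.
- The visit year is not settled. Section 5A (5.1.1, 5.1.2 and its Table 5-1) and Section 6.2 name 2012. Section 8A (8.2 and 8.7.5) names 2011 and 2013. With those two cohorts, each at 5/6 N, the detectable slopes would be about 0.013, 0.021 and 0.046, and power at the printed slopes about 91%. The printed figures would then be conservative.
- A reader might also infer that the remark on power in Section 5.1.2 is false. That remark is qualitative and does not cite Table 6.2. A detectable BMI-z slope of 0.0158 rather than 0.0150 per year can fairly be called no compromise.

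The mismatch between the table and the assumption printed with it survives all four.

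**Conclusion.** The T1D rows of Table 6.2 other than onset age were computed at constant N, contrary to the stated 5/6 N in 2012. Under that assumption the detectable slopes are about 5% larger (√(69.43/62.68) = 1.052), and power at the unrounded constant-N slopes is 75.9% instead of 80%. The shortfall at the printed slopes is about 3 to 4 points for BMI-z, HbA1c and insulin sensitivity, 1 to 2 points for C-peptide and autoimmunity, and none for DKA. Onset age and the type 2 rows are correct as printed.

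This rests on a two-sided 5% level carried over from Section 6.1 and on 2012 as the only Phase 3 visit cohort. It is a minor arithmetic inconsistency. The documents do not support reading it as a failure of the sampling design or of the study's power.

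**What to change.** First reconcile the visit years between Sections 5A and 6A (2012) and Section 8A (2011 and 2013).

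If 2012 stands, restate three T1D entries in Table 6.2: BMI-z 0.016, HbA1c 0.026, insulin sensitivity 0.056. C-peptide (0.008), autoimmunity (0.006) and DKA (0.006) stay as printed after rounding. If the visit years change, recompute all T1D and type 2 rows other than onset age for the new years. Section 5.1.2 needs no change to its remark on power.

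The cost is three table entries, which become slightly less favourable. Design, conduct and analysis are unaffected.
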